5.5.6 Rescue medication

Rescue medication is not permitted in this study.

5.5.7 Concomitant treatment

The investigator must consider the baseline and ongoing concomitant treatment in the core studies CAIN457A2304 or CAIN457A2307 at Week 52 before a subject enrolls in the extension study (CAIN457A2304E1).

The investigator should instruct the subject to notify the study site about any new treatments he/she takes after the start of study treatment. All medications and significant non-drug therapies (including physical therapy and blood transfusions) administered after the subject started study treatment must be listed on the Concomitant medications eCRF or Surgeries and Medical Procedures eCRF. Start date, end date, unit, frequency, route and reason for administration or change are to be recorded.

The investigator should instruct the patient to notify the study site about any new medications he/she takes after the patient was enrolled into the study. All medications, procedures and significant non-drug therapies (including physical therapy and blood transfusions) administered after the patient was enrolled into the study must be recorded.

5.5.8 Prohibited Treatment

The use of concomitant medication for psoriasis in all body regions (except face, scalp, and/or genitoanal area as noted below) is restricted to bland emollients (not supplied by Novartis) and other non-medicated interventions. Use of bland emollients must be recorded on the Concomitant medications eCRF.

The definition of “bland” excludes all topical medications that contain pharmacologically active ingredients such as (but not limited to) lactic acid, salicylic acid, urea, α -hydroxy acids or fruit acids.

The use of bland emollients should be avoided during the 12 hours preceding a scheduled study visit.

Topical corticosteroid (CS) treatment, or use of other topical treatment that is likely to impact signs and symptoms of psoriasis, is not allowed for treatment of psoriasis, except when applied to the face, scalp, and/or genitoanal area for \leq 14 consecutive days. Topical corticosteroid use for indications other than psoriasis not on an area affected with psoriasis is allowed for \leq 14 consecutive days.

Subjects need to be advised to limit exposure to ultraviolet (UV) light (including sunbathing and/or use of UV tanning devices) during the study to avoid possible effect on psoriasis.

The investigator should instruct the subject to notify the study site about any new treatments he/she takes after the start of the study treatment. All prohibited medications and significant non-drug therapies administered after the subject starts treatment with study treatment must be listed on the Concomitant medications eCRF or the Surgeries and Medical Procedures eCRF.

Use of any treatments displayed in [Table 5-4](#) that could confound the efficacy is NOT allowed for any indication during the study excluding treatment-free follow-up 2 period.

Table 5-4 Prohibited treatment

Prohibited treatments ^{†,‡}
Alefacept, briakinumab, efalizumab, ustekinumab
Biological immunomodulating agents other than above (e.g., adalimumab, etanercept, infliximab)
Other systemic immunomodulating treatments [§] (e.g., MTX, cyclosporine A, corticosteroids [§] , cyclophosphamide)
Other systemic psoriasis treatments* (e.g. retinoids, fumarates)
Photochemotherapy (e.g., PUVA)
Phototherapy (e.g., UVA, UVB)
Use of topical treatment that is likely to impact signs and symptoms of psoriasis for $>$ 14 consecutive days* (e.g., corticosteroids [CS], vitamin D analogues, pimecrolimus, retinoids, salicylvaseline, salicylic acid, lactic acid, tacrolimus, tar, urea, α -hydroxy or fruit acids)
Live virus vaccinations during extension study

Prohibited treatments^{†,‡}

Any investigational treatment or participation in any interventional clinical trial during extension trial

[†]If a subject inadvertently used the prohibited treatment in the core study (e.g. CAIN457A2304 or CAIN457A2307) without undue safety risk till completion of Week 52, eligibility will need to be discussed with the global clinical team.

[‡]In case of undue safety risk for the subject, the subject should discontinue study treatment at the discretion of the investigator. If the subject received a live virus vaccination during the study, the subject must discontinue study treatment.

[§]Inhalative CS with only a topical effect (e.g., to treat asthma) are not considered “systemic immunomodulating treatments” and are therefore acceptable as co-treatment

*There is no restriction on the use of anti-histamines or the use of corticosteroids in the eye or ear.

5.5.9 Discontinuation of study treatment and premature patient withdrawal

Subjects may voluntarily withdraw from the study for any reason at any time. They may be considered withdrawn if they state an intention to withdraw, fail to return for visits, or become lost to follow-up for any other reason.

Discontinuation from a treatment period

If premature withdrawal occurs for any reason, the investigator must make every effort to determine the primary reason for a subject's premature withdrawal from the study and record this information on the end of treatment (EOT) eCRF (Week 260).

Study treatment *must* be discontinued under the following circumstances:

- Withdrawal of informed consent
- Emergence of the following adverse events: adverse events that in the judgment of the investigator, taking into account the subject's overall status, prevent the subject from continuing participation in the study (for example, sepsis or serious infection).
- Any laboratory abnormalities that in the judgment of the investigator, taking into consideration the subject's overall status, prevents the subject from continuing participation in the study.
- Pregnancy (see [Section 6.5.6](#) and [Section 7.4](#))
- Continued use of prohibited treatment as per recommendations in [Table 5-4](#).
- Any other protocol deviation that results in a significant risk to the subject's safety

In addition to the requirements mentioned above for study treatment discontinuation, the investigator should discontinue study treatment for a given subject if, on balance, he/she believes that continuation would be detrimental to the subject's well-being.

Subjects who discontinue study treatment should NOT be considered withdrawn from the study. These subjects should have all Week 260 protocol assessments performed approximately four weeks after their last dose of secukinumab and then enter the treatment-free follow-up period (Weeks 264 and 268). Subsequently, these subjects should enter the follow-up 2 period. On the EOT eCRF (Week 260), the site staff must record the date and primary reason for stopping study treatment.

The investigator must contact the IRT when the subject completes the assessments on Week 260 due to study treatment discontinuation.

Study treatment must be discontinued after emergency unblinding.

The appropriate personnel from the study site and Novartis will assess whether study treatment should be discontinued for any subject whose treatment code has been broken inadvertently for any reason.

See [Section 6](#) for the required assessments of these subjects after study treatment discontinuation.

Withdrawal from a treatment-free period

If premature withdrawal occurs for any reason in the treatment-free follow up period or follow-up 2 period, the investigator must make every effort to determine the primary reason for a subject's premature withdrawal from the study and record this information on the applicable end of study period eCRF (Follow-up period completion eCRF [Week 268] or Follow-up 2 period completion eCRF, respectively).

Patients who withdraw from the follow-up period should perform the Week 268 assessments (see [Table 6-1](#)).

Premature subject withdrawal

Subjects who state an intention to withdraw prematurely from the study will be asked to return for follow-up visits to assess safety after cessation of therapy and, if willing, to assess duration of effect (e.g. rebound assessments). If the subject returns to the study site to have his/her follow-up visits, the investigator will follow the study treatment discontinuation procedures.

The investigator must contact the IRT when the subject completes the assessments on visit of Week 260 to register the subject's early completion of the study due to subject withdrawal.

Lost to follow-up

For subjects who are lost to follow-up (i.e. those subjects whose status is unclear because they fail to appear for study visits without stating an intention to withdraw), the investigator should show "due diligence" by documenting in the source documents steps taken to contact the subject, e.g. dates of telephone calls, registered letters, etc.

5.5.10 Emergency breaking of treatment assignment

Emergency treatment code breaks should only be undertaken when it is essential to treat the patient safely and efficaciously. Most often, study treatment discontinuation and knowledge of the possible treatment assignments are sufficient to treat a study patient who presents with an emergency condition. Emergency treatment code breaks are performed using the IRT. When the investigator contacts the system to break a treatment code for a patient, he/she must provide the requested patient identifying information and confirm the necessity to break the treatment code for the patient. The investigator will then receive details of the investigational drug treatment for the specified patient and a fax or email confirming this information. The system

will automatically inform the Novartis monitor for the site and the global study lead that the code has been broken.

It is the investigator's responsibility to ensure that there is a procedure in place to allow access to the IRT in case of emergency. The investigator will inform the patient how to contact his/her backup in cases of emergency when he/she is unavailable. The investigator will provide protocol number, investigational treatment name if available, patient number, and instructions for contacting the local Novartis CPO (or any entity to which it has delegated responsibility for emergency code breaks) to the patient in case an emergency treatment code break is required at a time when the investigator and backup are unavailable.

Study treatment must be discontinued after emergency unblinding.

The appropriate personnel from the study site and Novartis will assess whether study treatment should be discontinued for any subject whose treatment code has been broken inadvertently for any reason.

Subjects who are prematurely unblinded will be discontinued from the study treatment and requested to return for the end of the treatment period visit (Week 260), two follow-up visits and follow-up 2 period as described in [Section 3.1](#).

5.5.11 Study completion and post-study treatment

- A subject entering into CAIN457A2304E1 will be said to have completed the extension study after he/she has completed all visits and assessments as defined in [Table 6-1](#) and received all doses of the study treatment in accordance with the protocol.
- The extension study as a whole will be considered complete when all eligible subjects rolled over from the core study (e.g., CAIN457A2304 or CAIN457A2307) have completed as per protocol the visits and assessments defined in [Table 6-1](#) for study CAIN457A2304E1.

The investigator also must provide follow-up medical care for all subjects who are prematurely withdrawn from the study, or must refer them for appropriate ongoing care. Subjects who complete CAIN457A2304E1 may be eligible to enter another planned extension trial.

5.5.12 Early study termination

The study can be terminated at any time for any reason by Novartis. Should this be necessary, the patient should be seen as soon as possible and properly managed for a prematurely withdrawn patient. The investigator may be informed of additional procedures to be followed in order to ensure that adequate consideration is given to the protection of the patient's interests. The investigator will be responsible for informing IRBs and/or ECs of the early termination of the trial.

6 Visit schedule and assessments

[Table 6-1](#) Assessment Schedule lists all of the assessments and indicates with an "x" when the visits are performed.

Subjects should be seen for all visits on the designated day within the allowed “visit window” specified below or as close to it as possible.

During the treatment period, subjects may be seen at an unscheduled visit, e.g. if they experience deterioration of psoriasis, or AEs that in the opinion of the investigator need intervention or repeated laboratory testing. During these unscheduled visits, study treatment will NOT be administered. A visit window of “±5” will be allowed for Week 52 to Week 260 during the treatment period during the follow-up period or as close to it as possible.

Subjects who discontinue study treatment will continue to be followed for safety assessments. They are not considered withdrawn from the study.

Subjects who discontinue study treatment before completing the study, and those who prematurely withdraw from the study for any reason should be scheduled for a study visit 4 weeks after their last study treatment administration, at which time all the assessments listed for EOT (Week 260) will be performed (see [Section 5.5.10](#)). Subjects will return to the study site for further assessments as indicated under the follow-up visits (Weeks 264 and 268) (see [Section 3.1](#)).

Only subjects who prematurely discontinued study treatment should enter follow-up 2 period after completion of follow-up visits (Weeks 264 and 268). Follow-up 2 period includes telephone calls every 3 months until 4 years from the time subjects have been enrolled into CAIN457A2304E1 as well as potential unplanned assessments e.g physical examinations, vital signs and laboratory assessments during this time.

If they refuse to return for the needed assessments in the follow-up period or are unable to do so, every effort should be made to contact them or a knowledgeable informant by telephone or by sending appropriate correspondence (i.e. certified letter) immediately. At this contact, the safety (e.g., potential occurrence of AE or SAE) and the primary reason for a subject's premature withdrawal should be determined.

At a minimum, subjects will be contacted for safety evaluations during the 12 weeks following the last dose of study treatment, including final contact at the 12-week point. Documentation of attempts to contact the subject should be recorded in the subject record.

Order of assessments:

- Subject to complete QoL tools prior to any investigator assessments. Order of QoL tools is: DLQI, EQ-5D, HAQ-DI (subjects with history of PsA only but not applicable to subjects from the CAIN457A2307 core study)
- Investigator to complete investigator assessments. Order is:
 1. IGA
 2. PASI
- All remaining study visit procedures (e.g., laboratory sample collection, vital signs measurements) must be completed prior to study treatment dosing.
- Enter PASI and IGA assessments into eCRFs BEFORE contacting IRT at any scheduled visit
- Contact IRT to register the subject visit and receive study drug assignment.

Table 6-1 Assessment schedule

	Treatment Period (Years 1 and 2)																										Unscheduled visit		
	52 ^a Core	52 ^a Ext	56	60	64	68	72	76	80	84	88	92	96	100	104	108	112	116	120	124	128	132	136	140	144	148	152	156	
Week (Relative to Baseline of core studies)																													
Visit window (in days)	±5	±5	±5	±5	±5	±5	±5	±5	±5	±5	±5	±5	±5	±5	±5	±5	±5	±5	±5	±5	±5	±5	±5	±5	±5	±5	±5		
Day	365	365	393	421	449	477	505	533	561	589	617	645	673	701	729	757	785	813	841	869	897	925	953	981	1009	1037	1065	1093	
In office visit- all subjects	x	x	x	x	x	x	x	x	x	x	x	x	x	x	x	x	x	x	x	x	x	x	x	x	x	x	x		
Obtain informed consent	x																												
Inclusion/exclusion criteria ¹	x																												
Concomitant medications	x	x	x	x	x	x	x	x	x	x	x	x	x	x	x	x	x	x	x	x	x	x	x	x	x	x	x		
Physical examination	x	x	x	x	x	x	x	x	x	x	x	x	x	x	x	x	x	x	x	x	x	x	x	x	x	x	x		
Weight	x			x		x		x		x		x		x		x		x		x		x		x		x		x	
Vital signs	x		x	x	x	x	x	x	x	x	x	x	x	x	x	x	x	x	x	x	x	x	x	x	x	x	x		
Urinalysis (local)	x			x		x		x		x		x		x		x		x		x		x		x		x		x	
Lab analysis: chemistry and hematology ²	x		x	x	x	x	x	x	x	x	x	x	x	x	x	x	x	x	x	x	x	x	x	x	x	x	x		
Fasting Labs: lipid panel ²	x						x							x				x			x			x			x		
Fasting Labs: plasma glucose ²	x				x		x		x		x		x		x		x		x		x		x		x		x		
Serum pregnancy test ³	x																											x ³	
Urine pregnancy test (local) ⁴	x				x		x		x		x		x		x		x		x		x		x		x		x		
ECG (standard 12 lead)	x			x		x		x		x		x		x		x		x		x		x		x		x		x	
Blood sample for IG ^{5,6}	x					x							x				x			x			x				x		x ^{5,6}
Blood sample for PK ^{5,6}	x				x		x		x		x		x		x		x		x		x		x		x		x		x ^{5,6}
PASI	x		x	x	x	x	x	x	x	x	x	x	x	x	x	x	x	x	x	x	x	x	x	x	x	x	x		
IGA mod 2011	x		x	x	x	x	x	x	x	x	x	x	x	x	x	x	x	x	x	x	x	x	x	x	x	x			
Adverse event (AE) assessment	x		x	x	x	x	x	x	x	x	x	x	x	x	x	x	x	x	x	x	x	x	x	x	x	x			
EQ-5D	x			x		x		x		x		x		x		x		x		x		x		x		x		x	

Continue with Week 160

	Treatment Period (Years 3 and 4)																										Unscheduled visit ^{1,1}	Follow-up period		Follow-up 2 Period	
	160	164	168	172	176	180	84	188	192	196	200	204	208	212	216	220	224	228	232	236	240	244	248	252	256	260		264 /F4	268 /F8		
Week (Relative to Baseline of core studies)																															
Visit Window (in days)	±5	±5	±5	±5	±5	±5	±5	±5	±5	±5	±5	±5	±5	±5	±5	±5	±5	±5	±5	±5	±5	±5	±5	±5	±5	±5	±5				
Days	1121	1149	1177	1205	1233	1261	1289	1317	1345	1373	1401	1429	1457	1485	1513	1541	1569	1597	1625	1653	1681	1709	1737	1765	1793	1821					
In office visit if every 4 wks dosing			X			X			X				X			X			X			X							X	X	
Home administration if every 4 wks dosing	X	X		X	X		X	X		X	X	X		X	X		X	X		X	X		X	X	X						
In office visit if SoR dosing	X	X	X	X	X	X	X	X	X	X	X	X	X	X	X	X	X	X	X	X	X	X	X	X	X	X	X	X			
Concomitant medications	X	X	X	X	X	X	X	X	X	X	X	X	X	X	X	X	X	X	X	X	X	X	X	X	X	X	X	X			
Physical examination			X			X			X			X			X			X			X						X	(X)	X	X	
Weight																												X		X	
Vital signs	O	O	x	O	O	x1	O	O	x	O	O	O	x	O	O	x	O	O	x	O	O	x	O	O	O	x	O	x	x	x	
Urinalysis (local)			X			X			X			X			X			X			X						X		X		
Lab analysis: chemistry and hematology ²						X							X						X								X	X	X	X	
Fasting Labs: lipid panel ²																											X			X	
Fasting Labs: plasma glucose ²						X							X					X								X			X		

	Treatment Period (Years 3 and 4)																										Unscheduled visit ¹¹	Follow-up period	Follow-up 2 Period
	160	164	168	172	176	180	84	188	192	196	200	204	208	212	216	220	224	228	232	236	240	244	248	252	256	260			
Week (Relative to Baseline of core studies)	160	164	168	172	176	180	84	188	192	196	200	204	208	212	216	220	224	228	232	236	240	244	248	252	256	260			
Visit Window (in days)	±5	±5	±5	±5	±5	±5	±5	±5	±5	±5	±5	±5	±5	±5	±5	±5	±5	±5	±5	±5	±5	±5	±5	±5	±5	±5			
Days	1121	1149	1177	1205	1233	1261	1289	1317	1345	1373	1401	1429	1457	1485	1513	1541	1569	1597	1625	1653	1681	1709	1737	1765	1793	1821			
Serum pregnancy test ³																													
Urine pregnancy test (local) ⁴			x			x			x				x			x			x			x			x				
ECG (standard 12 lead)						x							x				x								x				
Blood sample for IG ^{5,6}													x												x	x ^{5,6}			
Blood sample for PK ^{5,6}													x												x	x ^{5,6}			
PASI	o	o	x	o	o	x	o	o	x	o	o	o	x	o	o	x	o	o	x	o	o	x	o	o	o	x	x	x	x
Assessment of rebound symptoms ⁷																									x	x ⁷	x	x	
IGA mod 2011			x			x			x				x			x			x			x			x	x	x	x	
Adverse event (AE) assessment	o	o	x	o	o	x	o	o	x	o	o	o	x	o	o	x	o	o	x	o	o	x	o	o	o	x	x	x	
DLQI			x			x			x				x			x			x			x			x				
HAQ-DI ⁸			x			x			x				x			x			x			x			x				
Serious AE assessment	o	o	x	o	o	x	o	o	x	o	o	o	x	o	o	x	o	o	x	o	o	x	o	o	o	x	x	x	
Complete PASI (and IGA ⁹) eCRF and call IRT	o	o	x	o	o	x	o	o	x	o	o	o	x	o	o	x	o	o	x	o	o	x	o	o	o	x	x	x	

	Treatment Period (Years 3 and 4)																										Unscheduled visit ¹¹	Follow-up period	Follow-up 2 Period
	160	164	168	172	176	180	84	188	192	196	200	204	208	212	216	220	224	228	232	236	240	244	248	252	256	260			
Week (Relative to Baseline of core studies)	160	164	168	172	176	180	84	188	192	196	200	204	208	212	216	220	224	228	232	236	240	244	248	252	256	260			
Visit Window (in days)	±5	±5	±5	±5	±5	±5	±5	±5	±5	±5	±5	±5	±5	±5	±5	±5	±5	±5	±5	±5	±5	±5	±5	±5	±5	±5			
Days	1121	1149	1177	1205	1233	1261	1289	1317	1345	1373	1401	1429	1457	1485	1513	1541	1569	1597	1625	1653	1681	1709	1737	1765	1793	1821			
Dispense Investigational Treatment ¹⁰	O	O	x	O	O	x	O	O	x	O	O	O	x	O	O	x	O	O	x	O	O	x	O	O	O	x			
End of Treatment Period (EOT) eCRF and call IRT																											x		
Follow-up Period completion eCRF																											x		
Follow-up 2 Period completion eCRF																											x		

eCRF:electronic case report form; PK:pharmacokinetics; IG:immunogenicity

O: assessment completed for subjects with protocol-mandated in-office visits in between Week 160 and 256.

*The screening period will be the duration between signing the informed consent form and enrollment registered with Interactive response technology (IRT). Subjects must sign the informed consent form after completing the core study Week 52 assessments.

^aEnrollment into the extension study occurs on the same day (Week 52) as the end of maintenance period of the core study CAIN457A2304 or CAIN457A2307 (±5 days). The column for Week '52 core' represents assessments that will be done during the CAIN457A2304 core Week 52 visit or the CAIN457A2307 Week 40 visit. These assessments will be entered in the core study eCRFs. The column Week '52 ext' represents assessments that will be done for the CAIN457A2304E1 study.

¹These assessments are supported by and are stored with the source documentation. However, data regarding to which Inclusion/Exclusion criteria are not met are captured on the Inclusion/Exclusion Screen eCRF.

²Samples will be shipped to and analyzed by the central laboratory.

³ To be done for female subjects of childbearing potential for whom local urine pregnancy test at end of maintenance period (Week 52) of core study is positive. The study drug treatment should not be given until the results confirm that subject is not pregnant.

⁴ If there is a positive urine pregnancy test, study treatment must be withheld and a serum pregnancy test must be done at the same visit.

⁵ Samples will be shipped by the sites and stored by the central laboratory. Samples will be shipped to reference laboratories for analysis. Each PK and IG sample is to be collected pre-dose for visits from Week 52 to Week 256.

⁶ An unscheduled IG and or PK sample is collected only to replace an IG or PK sample not taken at a regular scheduled visit. (If an IG sample is taken, a PK sample must accompany the IG sample.)

⁷ Unscheduled rebound assessment only to be done for an unscheduled visit that occurs during the treatment free follow-up period following a study drug discontinuation.

⁸ During this extension study, the HAQ-DI is completed only by subjects from core study CAIN457A2304 who have a history of psoriatic arthritis at the core baseline visit.

⁹ IGA eCRF only needs to be completed at visits when IGA is required

¹⁰ In subjects treated per SoR regimen, investigational treatment should only be dispensed and administered to patients meeting protocol-defined SoR treatment criteria

¹¹ During follow-up 2 period unscheduled visits may include unplanned assessments like physical examinations, vital signs and laboratory assessments if investigator considers this necessary.

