3.1 Study design

This is a multicenter, double-blind and open label, trial in subjects with moderate to severe chronic plaque-type psoriasis who completed treatment in the maintenance period of studies CAIN457A2304 or CAIN457A2307. It was expected that approximately 740 subjects would be enrolled at approximately 130 study sites worldwide. When recruitment was complete, 675 subjects had been enrolled at 112 sites.

This extension study consists of four periods: the screening period, the treatment period, and two follow-up periods (follow-up and follow up 2). An outline of the visits is presented in Figure 3-1, while a detailed visit schedule can be found in [Table 6-1](#).

Screening Period

The screening period for the extended maintenance portion of the study is the duration between the signing of the informed consent form and enrollment registered with the interactive response technology (IRT). There are no additional requirements for the treatment period other than subjects are required to complete year 1 of the core studies and all assessments at the end of maintenance visit (Week 52) of core study CAIN457A2304 or end of maintenance visit (Week 40) of core study CAIN457A2307. Subjects who complete the EOM visit and assessments of the core studies and consent to the extension will continue directly into the treatment period of this extension study. Subjects must sign the informed consent form (ICF) for the treatment period once the core assessments have been completed for Week 52 of the core studies and the IRT called to register that the subject completed the core study (CAIN457A2304 or CAIN457A2307). For the purpose of reading and understanding, the ICF can be provided to subjects anytime during the core studies, for example, between Week 48 and prior to the dose at Week 52 of study CAIN457A2304 (Weeks 36 and 40 from study CAIN457A2307 are equivalent to Weeks 48 and 52 of CAIN457A2304). However, subjects will NOT sign the ICF before completing the core studies' EOM assessments.

Note: subjects from CAIN457A2307 started their visits in that study after completing 12 Weeks of the CAIN457A2304 core study; therefore, Week 40 of the CAIN457A2307 study is equivalent to Week 52 of the CAIN457A2304 and CAIN457A2304E1 studies as regards previous treatment duration (i.e., 52 weeks).

The dose administered at Week 52 is the first dose of the CAIN457A2304E1 treatment period.

Treatment Period

The treatment period is defined as Weeks 52 through 260.

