6.1 Information to be collected on screening failures

All subjects who have signed an informed consent but who cannot or chose not to enter the CAIN457A2304E1 treatment period will be considered screen failures. If the subject discontinues before enrollment, the IRT must be called within two days and the reason for not being enrolled will be entered on the Screening Phase Disposition electronic Case Report Form (eCRF). The Screening visit date, Informed Consent eCRF, Inclusion/Exclusion Criteria eCRF must be completed. If the subject has any SAE in the screening period (between signing the ICF and being enrolled), the Adverse Event eCRF and a paper SAE form must be completed.

If a subject fails to be treated in the extension study, the subject completes the follow-up visits in the respective core study.

The Withdrawal of consent eCRF should be completed if consent was withdrawn during the screening period before the subject was enrolled. The Death eCRF should be completed in the case of a death during the screening period.

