Note: any AIN457 300mg (including AIN457 150mg FI switch to AIN457 300mg FI, AIN457 300mg FI, AIN457 150mg SoR switch to AIN457 300mg FI, AIN457 300mg SoR, AIN457 300mg SoR switch to AIN457 300mg FI and AIN457 300mg OL); any AIN 150mg (including AIN457 150mg FI and AIN457 150mg SoR); Any AIN457 including all the groups above.

The following study periods will be considered for analysis:

- **Extension study period:** Week 52 post-dose to Week 268;
- **Entire study period:** Combination of Induction (in A2304 core) period + Maintenance (in A2304 and in A2307) period + Core follow-up period (consider only for subjects who enter E1 after core follow-up period) + Treatment period in E1 [Initial Randomization in A2304 core to week 268] (including follow-up period);
- **Entire treatment period:** Combination of Induction (in A2304 core) period + Maintenance (in A2304 and in A2307) period + Core follow-up period (consider only for subjects who enter E1 after core follow-up period) + Treatment period in E1 [Initial Randomization in A2304 core to week 260]
- **Follow-up 2 period:** after W268 visit to end of the study.

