### **1.4 Assessment windows, baseline and post baseline definitions, missing data handling**

#### **1.4.1 Assessment windows**

No assessment windows have been defined for this study. Visit windows are described below.

If not otherwise specified, ‘first dose’, ‘randomization’ and ‘baseline’ are with respect to core study.

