#### **1.4.4 Visits windows**

*Visit-windows* will be used for the data that is summarized by analysis visit; they are based on the study evaluation schedule and comprise a set of days around the nominal visit day. For any assessment, there are the protocol defined scheduled visits around which visit windows were created to cover the complete range of days within the study. The visit windows are shown in [Table 1-8](#)

. In this table, the days are counted since the first dose of study treatment (study days) for safety assessments, and the days are counted since the date of randomization for efficacy assessments. These visit windows apply to measurements taken at every visit. For assessments collected less often different visit windows will be applied as detailed below.

When visit windows are used, all visits will be re-aligned, i.e., they will be mapped into one of the visit windows. E.g., if the *Week 4* visit of a subject is delayed and occurs on Day 46 instead of on Day 29, say, it will be re-aligned to visit window *Week 8*. In the case of major deviations from the visit schedule, or due to unscheduled visits, several assessments of a subject may fall in a particular visit window (either scheduled or unscheduled). Statistical approaches to handle multiple assessments in a given visit window are specified below.

Of note, subjects are allowed to have gaps in visits.

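### SAP 1.2 provides for subjects who enter the extension after core follow-up, which the protocol does not allow, and Table 1-8 has no rule for placing their visits

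*Protocol*

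**What the plan says.** **Protocol.** Entry is immediate. Section 3.1 says that consenting subjects who finish the end-of-maintenance visit "will continue directly into the treatment period of this extension study". Table 6-1, footnote a, says that enrolment "occurs on the same day (Week 52) as the end of maintenance period of the core study" and allows ±5 days. Core follow-up is for those who do not start extension treatment: under Section 6.1, if a subject is not treated in the extension, "the subject completes the follow-up visits in the respective core study".

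**SAP, study periods.** Section 1.2 defines an entire study period and an entire treatment period. Both definitions include "Core follow-up period (consider only for subjects who enter E1 after core follow-up period", so the SAP provides for a second, later route in.

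**SAP, visit windows.** Section 1.4.1 states that, unless otherwise specified, first dose, randomization and baseline "are with respect to core study". Under Section 1.4.4, safety windows run from that first core dose. Efficacy windows have their own anchor: "the days are counted since the date of randomization for efficacy assessments". The mapping goes by actual day, not by the visit name on the CRF: "When visit windows are used, all visits will be re-aligned, i.e., they will be mapped into one of the visit windows". Neither Section 1.4.4 nor Table 1-8 has an offset for late entry. Table 1-8 fixes extension Week 52 at Days 352–379 and ends at Day 1891.

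**SAP, main secondary efficacy analysis.** Section 1.8.1 applies the same windows to dosing dates, to decide whether a start-of-relapse (SoR) subject received active treatment at Weeks 92 and 144.

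**The concern.** The two documents disagree on when a subject can start the extension, and the windowing works only under the protocol's version. A subject who starts late has every extension visit shifted by the same number of days, while the windows stay fixed to core Day 1. By-visit PASI, IGA, laboratory, vital-sign and ECG values would then appear under a week that is not the protocol visit at which they were taken.

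Three places matter most:

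- **The end of treatment.** Week 260 is the last treatment-period visit.
- **The Week 156 switch.** After Week 156, Table 1-8 splits into two lists from Day 1108, which presumes that the switch visit took place around Day 1093.
- **Maintenance of response.** Windowed dosing dates and PASI values at Weeks 92, 104, 144 and 156 determine the result.

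The SAP recognises this kind of problem elsewhere. The end of Section 1.4.4 bars mapping between the induction and maintenance periods, but there is no matching rule at the boundary between core and extension.

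**Working it through.** **Inputs.** Scheduled days and windows come from SAP Table 1-8. Where several values share a window, the closest-to-target rule of Table 1-9 applies, with ties going to the earlier value. The delay *d* from core Week 52 to extension entry is not given. I assume 0–112 days, with 56 days as the central case because this extension's own follow-up ends 8 weeks after end of treatment. Scheduled visits are taken as on time, and core randomization and first dose as the same day. The 300 mg open-label group is not mapped after Week 156, because neither Table 1-8 list names it.

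**Step 1: reproduce the plan.** Scheduled day = 7 × week + 1.

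- Week 52: 7 × 52 + 1 = 365.
- Week 156: 7 × 156 + 1 = 1093.
- Week 260: 7 × 260 + 1 = 1821.

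These match Table 1-8. With *d* = 0, every scheduled visit falls in its own window: 37 of 37 in the fixed-interval (FI) and switch list, 55 of 55 in the SoR list.

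**Step 2: find the tolerance.** The Week 52 window ends at 379, and 379 − 365 = 14. The Week 260 window ends at 1835, and 1835 − 1821 = 14. Delays of up to 14 days, which cover the protocol's ±5, move nothing.

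**Step 3: shift the true Week 260 visit to Day 1821 + *d*.** The Week 264 window is Days 1836–1863 and the Week 268 window is Days 1864–1891.

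- *d* = 28: Day 1849, Week 264.
- *d* = 56: Day 1877, Week 268.
- *d* = 84: Day 1905, no window.

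**Step 4: see what fills the Week 260 cell.** The Week 260 window is Days 1766–1835 (FI/switch) or 1808–1835 (SoR). In the FI/switch list the true Week 244 visit is on Day 1709 + *d*. It enters that window once *d* ≥ 1766 − 1709 = 57.

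| Delay (days) | True Week 260 is analysed as | FI/switch Week 260 cell holds | SoR Week 260 cell holds |
|---|---|---|---|
| 0–14 | Week 260 | Week 260 | Week 260 |
| 15–42 | Week 264 | nothing | Week 256 |
| 43–56 | Week 268 | nothing | Week 252 |
| 57–70 | Week 268 | Week 244 | Week 252 |
| 71–98 | no window | Week 244 | Week 248 |
| 99–112 | no window | Week 244 | Week 244 |

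FI/switch visits still in their own window are 7 of 37 at 15–42 days, 2 of 37 at 43–56 days and 0 of 37 from 57 days. For SoR the count is 0 of 55 from 15 days.

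**Step 5: the switch visit (FI/switch list).** The Week 168 window is Days 1108–1219, target Day 1177.

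- *d* = 28: true Week 156 is on Day 1121 (56 days from target) and true Week 168 on Day 1205 (28 days from target). True Week 168 is used, so the label is right.
- *d* = 56: true Week 156 is on Day 1093 + 56 = 1149. True Week 168, on Day 1233, is outside the window. The pre-dose Week 156 value is reported as Week 168.
- *d* = 84: true Week 156 is on Day 1177, exactly on target, and is again reported as Week 168.

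**Step 6: maintenance of response.** Up to Week 156 the windows are 4 weeks wide. A delay of 56 days (8 weeks) therefore puts the true Week 84, 96, 136 and 148 visits into analysis Weeks 92, 104, 144 and 156. At 84 days (12 weeks) they are Weeks 80, 92, 132 and 144. In the SoR arms the active-treatment classification shifts too, because dosing dates are windowed in the same way.

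**The case against.** The strongest objection is that nothing shows any subject to be affected. The SAP clause is conditional, and under the protocol the group it describes should be empty. This stands: every consequence above is conditional, and its size in the trial cannot be derived.

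Second, the week labels count time from core baseline in both Table 1-8 and protocol Table 6-1. On that clock a shifted visit is correctly labelled. This also stands, but it does not settle the matter. The protocol visit, the switch and the end of treatment all follow the extension schedule, and the post-Week 156 lists take the switch time as fixed.

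Third, the reach is limited. The primary objective is safety. Adverse events are summarised over whole periods and yearly intervals, the worst-value laboratory summaries do not rest on single windows, and there is no hypothesis testing. All true. By-visit tables and maintenance of response remain exposed.

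A reader might infer that Week 260 is simply lost for late entrants. The windows do not support that as a general statement. The true Week 260 assessment is always displaced at 15 days or more, but the cell is empty only in the FI/switch groups at 15–56 days. Elsewhere in the assumed range an earlier visit is reported under that name.

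A reader might also infer that counting core follow-up in the entire treatment period materially inflates time on treatment. A2304 maintenance dosing runs to Week 48 (Day 337), and 337 + 84 = 421 = 365 + 56. Follow-up of up to 56 days after Week 52 is therefore already within the SAP's 84-day on-treatment rule. At 84 days only 449 − 421 = 28 days lie beyond it.

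**Conclusion.** The point holds as a conflict between the documents and a missing rule. The protocol has only same-day entry, SAP 1.2 twice allows for later entry, and the windowing has no provision for it. If any subject entered 15 or more days late, the true Week 260 assessment leaves its window in every case, and the Week 260 cell is either empty or holds an earlier visit. At delays such as 56 or 84 days, a value taken before any switched dose is reported as Week 168 in the FI/switch groups, and maintenance of response is judged on visits 8 or 12 weeks earlier in the extension than intended.

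This rests on an assumed delay and on there being at least one late entrant; the documents establish neither. It is not evidence that reported results are wrong. It is a reason to count these subjects and close the gap before the by-visit tables are relied on.

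**What to change.** 1. Count the subjects who entered after core follow-up, by arm, and report the number even if it is zero.
2. If there are none, delete the core follow-up clause from both period definitions in SAP 1.2. That removes the conflict with the protocol.
3. If there are some, reconcile this with the protocol's entry description and add one rule to SAP 1.4.4, with a cross-reference in 1.8.1. For these subjects, extension visits and dosing dates are mapped by nominal extension visit, or by days from the first extension dose set to Day 365. The rule should cover the by-visit analyses and the maintenance-of-response derivation. Either option restores the no-delay result (37 of 37 and 55 of 55).
4. State that core follow-up visits are kept out of the extension windows. Otherwise a core follow-up visit on, say, Day 393 would compete with a re-anchored Week 56 visit.
5. State that the adverse-event yearly intervals stay on core study days, so that the use of two clocks is explicit.

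There is no need to trim the entire treatment period at 84 days after the last core dose. The cost is SAP wording, one derivation rule and one count; no new data are required.
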